#### 5.4.5 Randomization

If the subject successfully meets eligibility criteria, the subject will be considered enrolled. At enrollment, the following activities will occur:

- The subject will move forward to randomization into one of two study groups (on a 1:1 allocation) as follows:
  - Group 1: will be instructed to take the following per label instructions for up to 8 days or until resolution of symptoms, whichever occurs first:

Product	Dose
Robitussin Maximum Strength Cough and Chest Congestion DM	Up to 20 ml*
*Not to exceed 6 doses in any 24 hour period.	

- Group 2: will be instructed to take the following per label instructions for up to 8 days or until resolution of symptoms, whichever occurs first:

Product	Dose
Robitussin Maximum Strength Cough and Chest Congestion DM	Up to 20 ml*
Robitussin Maximum Strength Nighttime Cough DM	Up to 20 ml*
*Not to exceed 4 doses of daytime + 1 dose of nighttime OR 3 doses of daytime + 2 doses of nighttime in any 24 hour period.	

- Upon group allocation, study team will arrange delivery of the study product(s).

- Once the delivery is successfully received, the subject will confirm receipt and usability of the product(s) via an online questionnaire directly entered into the EDC platform.
  - If unsuccessful (e.g. lost, damaged) study team will discuss with participant and arrange a new delivery if needed.

During the screening visit, subjects will be provided with dosing instructions and training on how to complete the assessment, questionnaires, and eDiaries. Subjects will be reminded to reach out to the study team with any questions or concerns.

## 5.5 Treatment Period

The number of days each subject will actively engage with the study will vary according to the resolution of their cough symptoms. Subjects will use the product(s) (as per label instructions) for up to 8 days unless they self-report that they are no longer seeking relief from their cough symptoms prior to that. If symptoms and subject reporting continues through Day 7, subjects will complete the daily questionnaires for 7 days (Day 1 - Day 7). Subjects with cough symptoms resolved sufficiently to no longer warrant product use or those who determine they no longer wish to medicate for cough symptoms will complete daily forms from baseline through one day after the last dose of study product(s). This will complete their “study period”.

The subject will receive links via text and email with instructions for completion of the study assessments. The subject will input their responses directly into the EDC platform during the study period:

- Subjects will report any changes in health, use of concomitant medications, or non-drug treatments/procedures
- Subjects will complete the WURSS-21 questionnaire, and specific QoL questions
- Subjects will complete an eDiary to record product use each day including:
  - product type taken
  - number of doses
- Subjects will self-report whether they are still seeking relief from their cough symptoms and answer end of the study questions prior to exiting the study.

## 5.6 End of Treatment Period

Robitussin product(s) may be used for up to 8 days (Day 0 - Day 7).

Subjects will have the option to discontinue treatment at their discretion. Subjects may choose to discontinue treatment if:

- they feel that their symptoms do not warrant further use of the study product(s), or
- their cough symptoms are considered resolved

Subjects that continue to use the study product(s) will be prompted to discontinue treatment after 8 consecutive days of use and seek advice from their general physician for further assessment and treatment.

Subjects will also be informed that the study will end on Day 7 (or the day after the last treatment, if earlier than Day 7), and will be asked to fill in an End of Study survey.

Subjects will be informed that a Change in Health survey will be sent 2 days after their last study product dose (day 9 at latest) and will be asked to report any changes in their health post-completion of the study.

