# 1 INTRODUCTION

## 1.1 Study Rationale

Real world evidence (RWE) studies offer an opportunity to gather information of a marketed product in real-world heterogeneous populations that can complement clinical evidence, consumer insight data, and post-marketing surveillance. Real world data (RWD) generation is increasingly important in determining effectiveness outside of the tightly controlled conditions of randomized controlled trials (RCTs), that do not always reflect real-world patient populations, limiting their generalizability and external validity (Sherman et al., 2016).

This decentralized study is designed to generate real world data from subjects with cough associated with the common cold, evaluating the effects in two arms with commercially available cough syrups on health-related quality of life. Arm 1 includes one cough syrup (which can be used day or night) and Arm 2 includes the daytime cough syrup and a nighttime cough syrup.

Robitussin Maximum Strength Cough and Chest Congestion DM (Dextromethorphan HBr, USP 20 mg; Guaifenesin, USP 400 mg) and Robitussin Maximum Strength Cough and Chest Congestion DM + Robitussin Maximum Strength Nighttime Cough DM (Dextromethorphan HBr, USP 30 mg; Doxylamine Succinate, USP 12.5 mg) are marketed cough and congestion syrups used for treatment of cough associated with common cold. Although this is a non-life-threatening condition, it impacts individuals' ability to function normally in day-to-day activities (physical, social, occupational, and emotional).

Based on a large national on-line survey conducted in the United States (ACHOO survey) (Blais et al., 2015, Dicpinigaitis et al., 2015), Cough was the most common cold symptom (73.1%) and had a delayed onset (typically 1–5 days after cold onset) and a long duration (>6 days in 35.2%). Nasal congestion and cough were the most bothersome symptoms (Blais et al., 2015). Overall, 93% of survey participants reported sleep difficulty (slight to extreme) during a cough/cold. Among all respondents, 57% reported cough or nasal congestion as the symptoms making sleep difficult (Dicpinigaitis et al., 2015). In a similar RWE study, it was demonstrated that associated cold symptoms like blocked nose can impact overall quality of life and also that treatment can provide clinically meaningful improvements in QoL.

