## 7.2 Product Supplies, Product Storage, Accountability, Returns and Destruction

Study products are to be dispensed only to subjects enrolled in the study in accordance with the protocol, by delegated study staff. Enrolled/randomized subjects will be informed on product usage and storage and what to do in the event of product loss when the products are first dispensed.

All study products supplied are for use only in this clinical study and should not be used for any other purpose.

Orders for study product(s) are to be placed immediately following randomization for delivery to subjects. Given this delivery model and the shelf stability of the product(s), a formal accountability form/record will not be maintained, however trained study staff will maintain an order and delivery tracker.

At the end of the study, subjects may retain any remaining/unused study product(s).

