### 9.3 Time Period and Frequency for Collecting AE and SAE Information

All AEs, and therefore all SAEs (except from those exempt from recording, as described in section 9.1 and section 9.2) will be collected from immediately after a subject is randomized within the trial and until 2 days following the last administration of study product.

A change in health survey will be released to subjects 2 days after their last study product(s) dose. If a subject reports a change in health, a member of the study team will reach out to record the relevant details.

Medical occurrences that began before randomisation will be recorded in the Medical History/Current Medical Conditions section of the Electronic Case Report Form (eCRF), not the AE section.

Details recorded by the subject that meet the definition of a serious AE must be discussed with the subjects and transcribed into the SAE section of the eCRF

All SAEs will be recorded and reported to the sponsor or designee immediately, and under no circumstance should this exceed 24 hours. The investigator will submit updated SAE data to the sponsor within 24 hours of it being available.

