## 9.11 Pregnancy

### 9.11.1 Time Period for Collecting Pregnancy Information

Pregnancy information will be collected on all pregnancies reported while a female subject is participating in the study from the date/time of signing the informed consent until 5 days after the last administration of the study product.

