4.4.1 Study Product Compliance and Exposure

Compliance will be assessed as the number of days subjects reported to have adhered to the treatment regime up the end of treatment. For compliance and analysis tables, the end of treatment will be defined as the last day the subject used the study product or day 7. The number of compliant days will be tabulated using absolute and relative frequencies as well as the mean, standard deviation, minimum and maximum values, median, and quantiles (Table 14.1.6 and Listing 16.2.5.1). A summary of daily product use will also be presented (Table 14.1.7 and Listing 16.2.5.1). Listing 16.2.5.1 will show all study product uses, including subjects who use the study product after Day 7.

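### The Day 9 limit on the final safety survey conflicts with an AE window that runs from the last dose, and the 5-day pregnancy window has no scheduled contact at its end

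*Protocol*

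**What the plan says.** **Windows.** Protocol section 9.3 collects AEs and SAEs from randomization "until 2 days following the last administration of study product". Section 9.11.1 collects pregnancies from consent "until 5 days after the last administration of the study product".

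**Scheduled contacts.** Section 5.5 and Table 5-1 schedule the daily forms up to Day 7. The last contact is the Change in Health survey. Section 9.3, footnote j and the last column of Table 5-1 all place it 2 days after the last dose and give no latest date. Section 5.6 adds one: "Change in Health survey will be sent 2 days after their last study product dose (day 9 at latest").

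**Length of use.** Section 5.6 states: "Robitussin product(s) may be used for up to 8 days (Day 0 - Day 7"). The same section says that continuing users will be "prompted to discontinue treatment after 8 consecutive days of use". Table 5-1 footnote g has product shipped only after the baseline assessments and confirmed eligibility. Section 3.4 calls Day 7 a tentative end of treatment. Section 7.2 says that "subjects may retain any remaining/unused study product(s").

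**Use after Day 7.** SAP section 4.4.1 plans a listing of all product uses, "including subjects who use the study product after Day 7". SAP section 4.5.1.1 keeps timepoints after Day 7 out of the analysis tables but in the listings.

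**The concern.** Both collection windows move with the last dose. The daily forms do not, and under section 5.6 neither does the latest date of the survey. A subject who doses after Day 7 could therefore receive the final survey before the stated AE window has closed. With a last dose on Day 9 the survey would arrive that same day, and with a later last dose it would arrive while the subject was still dosing. Section 5.6 cannot be programmed together with section 9.3 and footnote j for such a subject.

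There is little behind the survey to catch a late event. The lost-to-follow-up procedure in section 10.1.2 starts from two missed diaries and cannot start once no diary is due. The calls in section 5.8 concern AEs already reported. Section 9.8 places no duty on the investigator to look for AEs after participation ends.

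The pregnancy window raises a separate question, because its stated end lies beyond any scheduled contact whenever the last dose is taken. In both cases the report could describe a collection window longer than the one that was actively followed.

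**Working it through.** **Inputs.** Permitted use is Day 0 to Day 7 (5.6). The AE window ends at last dose + 2 (9.3) and the pregnancy window at last dose + 5 (9.11.1). The survey is sent at last dose + 2, with a latest date of Day 9 in 5.6 only. The last daily form is on Day 7 (5.5, Table 5-1).

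**The plan's own figure.** Day 0 to Day 7 is 8 days. The latest survey is 7 + 2 = Day 9, so the stated figure reproduces for permitted use.

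**Formulas.** Let L be the day of the last dose.
- AE window end = L + 2.
- Pregnancy window end = L + 5.
- Survey day = min(L + 2, 9) under 5.6, or L + 2 under 9.3 and footnote j.
- Gap = window end − survey day.

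**Results with the Day 9 limit.**

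| Last dose | Survey | AE window ends | AE gap (days) | Pregnancy window ends | Pregnancy gap (days) |
|---|---|---|---|---|---|
| Day 5 | Day 7 | Day 7 | 0 | Day 10 | 3 |
| Day 7 | Day 9 | Day 9 | 0 | Day 12 | 3 |
| Day 8 | Day 9 | Day 10 | 1 | Day 13 | 4 |
| Day 9 | Day 9 | Day 11 | 2 | Day 14 | 5 |
| Day 10 | Day 9 | Day 12 | 3 | Day 15 | 6 |
| Day 11 | Day 9 | Day 13 | 4 | Day 16 | 7 |

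**Results without the limit.** The AE gap is (L + 2) − (L + 2) = 0 and the pregnancy gap is (L + 5) − (L + 2) = 3 days, for any L.

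**How a last dose can fall after Day 7.** With a first dose on Day k, the eighth consecutive day of use is Day k + 7. For k = 0 this is Day 7, and the two statements in 5.6 agree. For k = 1, 2, 3 or 4 it is Day 8, 9, 10 or 11, with 1 to 4 days of use after the last scheduled form. The documents give no delivery time, so a lag of 1 to 4 days is an assumption. The calculation also takes Day 0 as the virtual visit, as Table 5-1 labels it. Section 6.1 starts the daily links at product receipt, so this anchor is not fully settled.

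**The case against.** The strongest reply is that Day 9 is simply 7 + 2. It describes permitted use, and three other places give the survey no latest date. That stands: a reader might infer that the last contact is fixed at Day 9 whatever the last dose, and the documents do not say so. An AE gap needs both use after Day 7 and the Day 9 limit prevailing over the other passages. The conflict remains, because the SAP foresees such use.

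A reader might also try to size the problem from section 1.1, where cough had "a long duration (>6 days in 35.2"%): 0.352 × 200 ≈ 70 completers, or 0.352 × 260 ≈ 92 enrolled. The documents do not support this. The figure is a survey result on cough duration. Entry is within 48 hours of cough onset, so six days of cough falls at about Day 4 to Day 6. The figure shows neither symptoms at Day 7 nor dosing after it, and any share assumed to keep dosing would have no source.

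Two further inferences fail.
- It is not shown that late use goes unrecorded, because the SAP listings imply that some records after Day 7 exist. SAP section 5 does describe diaries that kept going out, but after treatment had stopped; that does not itself show entries after Day 7.
- It is not shown that late dosers have the least safety follow-up. Someone dosing through Day 7 has seven daily checks plus the survey, more than someone who stops early. Section 9.5 also lets subjects report AEs at any point during the study, and section 9.8 requires notification of related SAEs learned of later.

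The effect on the main tables is limited. The safety endpoint is AEs while on treatment, and the SAP tabulates treatment-emergent AEs without naming a rate up to 2 days after the last dose.

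On pregnancy, section 9.11.1 can be read as governing reports received rather than promising a contact, and sections 5.3.2 and 6.2.1 rely on the subject to report. That also stands, so the shortfall is one of active ascertainment. But section 6.2.1 asks for reports during the study, and section 5.6 tells subjects that the study ends on Day 7 or earlier.

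**Conclusion.** The point holds as a conflict between passages with a bounded effect on safety ascertainment. There is no AE gap for dosing within Day 0 to Day 7. Under the section 5.6 limit, each day of dosing beyond Day 7 leaves one further day of the stated AE window after the final scheduled contact, which is 1 to 4 days for a last dose on Day 8 to Day 11. This range rests on Day 0 being the virtual visit and on an assumed delay of 1 to 4 days before first use, or on use beyond the scheduled period for another reason. The number of subjects affected cannot be computed, because the documents give neither the delivery time nor the share dosing after Day 7.

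The pregnancy shortfall is a separate matter and needs no such assumption. It is 3 days for every female subject, whenever she stops, and rises to 4 to 7 days in the late-dosing cases if the Day 9 limit is applied. During those days only subject-initiated reporting is available.

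**What to change.** 1. Remove the Day 9 limit from section 5.6 so that it agrees with section 9.3 and Table 5-1 footnote j.
2. On the Day 7 form and on the survey, ask for the date of the last dose and whether product is still being taken. Send the survey 2 days after the reported last dose, and continue a short product-use and AE form until then.
3. For pregnancy, either add one message at 5 days after the last dose or set the stated window to the last contact.
4. State in Table 5-1 whether study days count from the virtual visit or from product receipt.
5. The sponsor must reconcile the two descriptions of the treatment period in section 5.6, one in study days and one in consecutive days of use. No treatment or stopping rule is proposed here.

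If data collection is already over, list last-dose and survey dates for subjects who used product after Day 7, and describe the windows actually covered.

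The cost is one or two ePRO questions, a changed send trigger and revised wording. A few subjects would stay in contact some days longer.

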## 5.7 Study Conclusion

The Study Conclusion page of the eCRF will be completed for all subjects by the study team.

If a subject experiences any AEs Haleon will be notified. AEs may be marked as unresolved and local study PI will ask the subject to seek appropriate professional healthcare, if applicable.

## 5.8 Follow-Up Phone Call

The study team will contact a subject to follow up on any reported ongoing AE/SAE post-study completion/withdrawal to ensure any issues are resolved as soon as possible. The study team must make every effort to regain contact with the subject (where possible, 3 contacts).

Should the subject continue to be unreachable, the AE/SAE will be considered unresolved.

Consistent with the treatment period, any reports that are collected on the WURSS-21 symptom domain assessment are not to be considered as AEs.

Refer to section [9.8](#) Follow-up of AEs and SAEs for more information.

# 6 STUDY ASSESSMENTS

Every effort should be made to ensure that protocol-required assessments and procedures are completed as described. However, it is anticipated that from time to time there may be circumstances outside the control of the investigator that may make it infeasible to complete an assessment. When a protocol-required assessment cannot be performed, the investigator (or designee) will document the reason for the missed assessment as a protocol deviation and any corrective and preventative actions that he or she has taken to ensure that required processes are adhered to as soon as possible. The Sponsor must be informed of any missed assessments.

## 6.1 Outcome Assessments

Assessments will be performed by delegated staff at the times, and in the order, defined in the Study Procedures section of this protocol.

The primary objective of the study is to evaluate the over-time effects of two Robitussin Maximum Strength products on QoL factors and common cold symptoms among individuals experiencing cough associated with common cold, following up to 8 days of treatment using WURSS-21.

Links will be sent to the subject daily for self-completion of the following quality of life tools from receipt of product to study conclusion.

- WURSS-21 Questionnaire (in appendix section [14.3](#))
- Additional QoL Questions (in appendix section [14.3](#))

## 6.2 Safety and Other Assessments

The following safety assessments will be performed by appropriately trained staff/clinical examiners, at the times and in the order defined in the Study Procedures section of this protocol.

6.2.1 Pregnancy Testing

There is no pregnancy warning on labeling, a pregnancy test will not be required.

Female subjects will provide verbal confirmation of pregnancy status at Screening (Virtual Visit) and will be asked to inform study staff immediately should this change at any point during the study. Female subjects who are pregnant or intending to become pregnant during the study (self-reported) will not participate further in the study.

7 STUDY PRODUCTS

For the purposes of this study, per International Conference on Harmonization (ICH) guidelines, and Haleon policy, study intervention is defined as any investigational intervention(s), marketed product(s), placebo, or medical device(s) intended to be administered to a study participant according to the study protocol. This includes a product with a marketing authorization when used or assembled (formulated or packaged) in a way different from the approved form, or when used for an unapproved indication, or when used to gain further information about an approved use.

As the study product(s) will be purchased from the local retailer, no study label will be required.

7.1 Study Product Supplies

Each subject will receive sufficient study product(s) to cover usage during the treatment period of the study. The following study products will be supplied by the CRO’s preferred vendor ([Table 7-1](#)). Study product(s) usage instructions are consistent with the commercially available pack instructions. Subjects will not be required to return or destroy used/unused study products after treatment discontinuation, completion of study or withdrawal.

Table 7-1 Investigational/Study Product Supplies

	Group 1	Group 2 (Product 1 + Product2)
Product Name	Robitussin Maximum Strength Cough and Chest Congestion DM	Robitussin Maximum Strength Cough and Chest Congestion DM  Robitussin Maximum Strength Nighttime Cough DM
Pack Design	Labeled commercial pack	Labeled commercial pack
Dispensing Details	Shipped to subject upon randomization	Shipped to subject upon randomization
Haleon formula codes:	CCI	CCI
Dose and usage Instructions	Up to 20 ml, not to exceed 6 doses in any 24-hour period.	Up to 20 ml per dose. Not to exceed 4 doses of daytime + 1 dose of nighttime

		OR 3 doses of daytime + 2 doses of nighttime in any 24-hour period.
Route of Administration	Oral	Oral
Return Requirements	All unused/used study products will not be returned	All unused/used study products will not be returned

\*See dosing instructions in [Section 5.4.5](#)

## 7.2 Product Supplies, Product Storage, Accountability, Returns and Destruction

Study products are to be dispensed only to subjects enrolled in the study in accordance with the protocol, by delegated study staff. Enrolled/randomized subjects will be informed on product usage and storage and what to do in the event of product loss when the products are first dispensed.

All study products supplied are for use only in this clinical study and should not be used for any other purpose.

Orders for study product(s) are to be placed immediately following randomization for delivery to subjects. Given this delivery model and the shelf stability of the product(s), a formal accountability form/record will not be maintained, however trained study staff will maintain an order and delivery tracker.

At the end of the study, subjects may retain any remaining/unused study product(s).

